4.3. Exclusion Criteria

A patient will not be eligible for inclusion in this study if any of the following criteria apply:

1. Patients with lymphangioleiomyomatosis (LAM) are excluded.
2. Known active uncontrolled or symptomatic CNS metastases. A patient with controlled and asymptomatic CNS metastases may participate in this study. As such, the patient must have completed any prior treatment for CNS metastases ≥ 28 days (including radiotherapy and/or surgery) prior to start of treatment in this study and should not be receiving chronic corticosteroid therapy for the CNS metastases.
3. Active gastrointestinal bleeding.

4. Pre-existing thyroid abnormality is allowed provided thyroid function can be controlled with medication.
5. Uncontrolled serious medical or psychiatric illness. Patients with a “currently active” second malignancy other than non-melanoma skin cancers, carcinoma in situ of the cervix, resected incidental prostate cancer (staged pT2 with Gleason Score ≤6 and postoperative PSA <0.5 ng/mL), or other adequately treated carcinoma-in-situ are ineligible. Patients are not considered to have a “currently active” malignancy if they have completed therapy and are free of disease for ≥1 year).
6. Liver-directed therapy within 2 months of enrollment. Prior treatment with radiotherapy (including radio-labeled spheres and/or cyberknife, hepatic arterial embolization (with or without chemotherapy) or cyrotherapy/ablation) is allowed if these therapies did not affect the areas of measurable disease being used for this protocol.
7. Recent infection requiring systemic anti-infective treatment that was completed ≤14 days prior to enrollment (with the exception of uncomplicated urinary tract infection or upper respiratory tract infection).
8. Uncontrolled diabetes mellitus as defined by HbA1c >8% despite adequate therapy.
9. Unstable coronary artery disease or myocardial infarction during preceding 6 months.
10. Receiving any concomitant antitumor therapy.
11. Patients with history of interstitial lung disease and/or pneumonitis, or pulmonary hypertension.
12. Use of strong inhibitors and inducers of CYP3A4 within the 14 days prior to receiving the first dose of ABI-009. Additionally, use of any known CYP3A4 substrates with narrow therapeutic window (such as fentanyl, alfentanil, astemizole, cisapride, dihydroergotamine, pimozide, quinidine, terfanide) within the 14 days prior to receiving the first dose of ABI-009.
13. Known Human Immunodeficiency Virus (HIV).
14. Active Hepatitis B or Hepatitis C.

5. TABLE OF EVENTS

The schedule of assessments in [Table 2](#) outlines the specific time points for study assessments.

Table 2: Schedule of Assessments

Assessment ^a	Screening ^b (Day -14 to - 1)	Cycle 1 through Last Cycle (Treatment Period)		End of Treatment (EOT) Visit ^d	Follow-up Period ^e
		Day 1 ^c	Day 8		
General Assessments, Biomarkers, PK samples					
Informed Consent	X				
Demographics	X				
Medical History	X				
Physical Examination	X	X		X	
Vital Signs, Height and Weight	X	X ^f	X ^f	X ^f	
BSA Calculation		X ^m			
Prior/Concomitant Medication Evaluation ^g	X	X	X	Until 28 days after the last dose of IP	
Prior/Concurrent Procedures Evaluation ^g	X	X	X	Until 28 days after the last dose of IP	
ECOG PS	X	X		X	
Pregnancy Test ^h	X			X	
ECG (12 lead) ⁱ	X	X	X		
Survival status					X
Pre-treatment tissues (archival or fresh) (mandatory) ^j	X				
Tumor biopsy for Biomarkers ^k	X	Upon disease progression and/or end of last dose of IP			
Blood Sample for Biomarkers	X	Cycle 4/D1 and Upon disease progression and/or end of last dose of IP			
Blood Sample for Rapamycin (PK) ^l		Pre-treatment and at 0.5, 1, 2, 4 hrs post- treatment	Pre-treatment and at 0.5, 1, 2, 4 hrs post- treatment		
Adverse Events	Continuous starting from signing of Informed Consent until 28 days after last dose of IP				

Assessment ^a	Screening ^b (Day -14 to - 1)	Cycle 1 through Last Cycle (Treatment Period)		End of Treatment (EOT) Visit ^d	Follow-up Period ^e
		Day 1 ^c	Day 8		
ABI-009 Dosing		X	X		
Local Laboratory Assessments					
Clinical Chemistry Panel	X	X		X	
CBC, Differential, Platelet Count	X	X	X	X	
PT, PTT, INR	X				
Urinalysis	X				
Thyroid function	X	X			
HIV, HBV sAg, HBV cAb, HCV Ab	X				
Fasting Lipids	X	X ⁿ			
Imaging and Efficacy Assessments					
CT/MR ^o	X	Every 6 weeks after C1 D1 for the first year, then every 12 weeks thereafter		X	

- a. Unless otherwise specified, visits must occur within \pm 2 days of the planned visit date.
- b. Screening evaluations to be obtained \leq 14 days prior to enrollment unless specified otherwise.
- c. Day 1 evaluations can be omitted if screening evaluations are performed within 72 hours of Cycle 1 Day 1.
- d. End of Treatment Visit must occur at least 4 weeks (\pm 7 days) after the last dose of ABI-009.
- e. Follow-up for survival and initiation of anticancer therapy can be performed by telephone contact every 12 weeks (+/- 3 weeks) or more frequently if needed, from EOT Visit. All patients that discontinue study drug and have not withdrawn full consent to participate in the study will continue in the follow-up phase for survival and anticancer therapy. This evaluation may be made by record review and/or telephone contact.
- f. Vitals and weight only.
- g. Prior: record all medications taken and procedures done \leq 28 days prior to screening; Concomitant: any medications or procedures after the signing of informed consent.
- h. For females of childbearing potential only. A serum β -hCG pregnancy test must be performed to assess patient eligibility at screening prior to first IP administration (negative results required for IP administration). Urine pregnancy test will be performed at EOT Visit (can be done locally) and as clinically indicated as per institutional guidelines.
- i. ECG to be monitored at screening, Cycle 1 Day 1 and Day 8, and thereafter on Day 1 of every treatment Cycle. In each case ECG is to be monitored during infusion around the 30 min time point after start of infusion to coincide with the end of infusion period which lasts 30 minutes (+/- 10 min).
- j. Ensure the surgical pathology report is submitted with tumor tissue sample (either tumor block or unstained slides [min 6]).
- k. Biopsy tumor sample: formalin-fixed, paraffin-embedded (FFPE) tumor tissue or unstained slides from biopsy will be collected (tumor blocks are preferred – refer to Instruction Sheet for details). Screening tumor tissue (fresh/archival) required for biomarker analysis for all patients. On study tumor tissue collection is optional only for patients who provide additional consent.
- l. PK samples to be taken only at Cycle 1 on Day 1 and Day 8 (pre-treatment and at 0.5, 1, 2, and 4 hrs (+/- 10 min) post-treatment) and in Cycle 2 Day 1, when only a pre-treatment sample is required.
- m. Calculated ONLY on C1/D1; to be recalculated only if the weight changes by $>$ 10% in subsequent cycles.
- n. Every even numbered cycle starting with Cycle 2, eg C2, C4, C6, etc.

- o. Screening CT/MRI scans must be performed within 28 days prior to study day 1, preferably as close to the day of enrollment as possible. Tumor evaluation by contrast-enhanced CT or MRI of the chest, abdomen, and pelvis will be performed during screening; every 6 weeks (\pm 3 days after C1D1 for the first year then every 12 weeks (\pm 7 days) thereafter until disease progression. EOT visit CT/MRI should be performed only for those patients that discontinue treatment for a reason other than disease progression per RECIST 1.1. If an initial observation of objective response (CR or PR) is made, a confirmation scan should be done at 6 weeks after initial observation.

6. PROCEDURES

6.1. Screening Evaluations

This study will be conducted at approximately 10 sites in the US. Additional sites may be added.

Each patient who enters into the screening period for the study receives a unique patient identification number before any study-related procedures are performed. The patient identification number will be assigned. This number will be used to identify the patient throughout the clinical study and must be used on all study documentation related to that patient.

The patient identification number must remain constant throughout the entire clinical study; it must not be changed after initial assignment, including if a patient is rescreened.

Before patients may be entered into the study, the Sponsor requires a copy of the site's written IRB/IEC approval of the protocol, informed consent form, and all other patient information and/or recruitment material, if applicable. A signed and dated Institutional Review Board (IRB) approved informed consent form (latest approved version) must be obtained from each patient prior to performing any study-specific procedures. All patients or legally acceptable representatives must personally sign and date the consent form before commencement of study-specific procedures. Adverse Events are to be collected for a patient once they are signed the informed consent. The patients' tumor samples will be tested to confirm diagnosis and for biomarker analyses after informed consent form has been signed.

Screening evaluations will be performed for all patients to determine study eligibility. These evaluations must be obtained ≤ 14 days prior to enrollment. Any questions regarding patient eligibility should be directed to AADI or other sponsor-nominated representatives or designees for approval.

The following procedures are to be completed during the screening period, after signed informed consent has been obtained, designated in the Schedule of Assessments, [Table 2](#).

- Demographics (if allowed by local regulations, date of birth, sex, race, and ethnicity)
- Physical examination as per standard of care (including physical exam, medical/cancer history, ECOG performance status assessment, height, weight)
- Prior/concomitant medication evaluation: all medications taken ≤ 28 days prior to screening
- Prior/concurrent procedures evaluation: all procedures done ≤ 28 days prior to screening

- Vital signs (eg, blood pressure, pulse, respiration rate, temperature)
- ECG
- Informed consent signed to collect for pre-treatment tumor sample (archived or fresh) along with pathology report for diagnosis confirmation and biomarker study for all patients
- Adverse event assessment
- Local Laboratory Assessments: chemistry, complete blood count (CBC), differential, platelet count, coagulation, urinalysis, thyroid function, pregnancy test (women of child-bearing potential, includes tubal ligations), HIV, hepatitis B surface antigen, hepatitis C antibody, fasting lipids
- Urinalysis (a urine dipstick may be used)
- CT or MRI, must be performed within 4 weeks prior to study day 1, preferably as close to the day of enrollment as possible

A patient is considered enrolled when the investigator decides that the patient has met all eligibility criteria. The investigator is to document this decision and date, in the patient's medical record and in/on the electronic case report form (eCRF).

All screening tests and procedures must be performed within 14 days of study day 1, unless specified otherwise in the study procedures listed in [Section 5](#). Once eligibility is confirmed, a site representative will complete and fax a patient eligibility criteria worksheet/tumor biopsy reference form to an AADI representative. The AADI representative will acknowledge receipt of the paperwork and confirm enrollment for that individual patient.

6.2. Treatment Period

A patient is considered enrolled on study day 1 when the IP, ABI-009, is first administered. ABI-009 is to be administered after all other protocol-specified pre-dose assessments have been performed during each visit that it is required. Patients will continue therapy until disease progression or unacceptable adverse events.

6.2.1. Day 1 Assessment

The following assessments will be performed on Day 1 of each cycle, unless otherwise specified:

- Physical examination
- Weight assessment
- BSA calculation (Calculated ONLY on C1/D1; to be recalculated only if the weight changes by > 10% in subsequent cycles)
- Concomitant medication and procedures evaluation
- Vital signs (temperature, systolic and diastolic blood pressure, and pulse)
- ECOG performance status

- ECG (12-lead ECG is to be conducted during infusion around the 30 min time point after start of infusion to coincide with the end of infusion period which lasts 30 minutes [+/- 10 min]). Day 1 ECG is conducted for every cycle.
- Clinical chemistry panel (including but not limited to sodium, potassium, chloride, glucose, alkaline phosphatase (ALP), AST/SGOT, ALT/SGPT, serum albumin)
- CBC, differential and platelet count
- Thyroid function
- Fasting lipids (every even numbered cycles starting with Cycle 2)
- Adverse Event assessment
- Pharmacokinetics assessment (only on Cycle 1 Day 1 at pre-treatment and at 0.5, 1, 2, 4 hrs post-treatment and Cycle 2 Day 1 at pre-treatment only)

Day 1 evaluations for Cycle 1 may be omitted if screening evaluations are performed within 72 hours of Cycle 1 Day 1. Laboratory assessments: chemistry, hematology, coagulation, urinalysis, pregnancy test (women of child-bearing potential, includes tubal ligation) (see [Table 3](#) for analyte listing).

6.2.2. Day 8 Assessment

The following assessments will be performed on Day 8 of each cycle, unless otherwise specified:

- Concomitant medication and procedures evaluation
- Vital signs
- CBC, differential and platelet count
- Adverse Event assessment
- Pharmacokinetics assessment (only on Cycle 1 Day 8 pre-treatment and at 0.5, 1, 2, 4 hrs post-treatment)
- ECG (12-lead ECG is to be conducted during infusion around the 30 min time point after start of infusion to coincide with the end of infusion period which lasts 30 minutes [+/- 10 min]). Day 8 ECG is conducted only on Cycle 1.

6.2.3. Response Assessment

Tumor response will be assessed by CT or MRI scan of the chest, abdomen, and pelvis; image preparation and evaluation will follow the specifications provided in the RECIST version 1.1. The same modality (CT or MRI) must be used at screening and throughout the study.

CT/MRI scans to be performed at the following frequency:

- ≤4 weeks prior to C1D1 (screening)

- followed by every 6 weeks after C1D1 for the first 1 year (\pm 3 days)
- followed by every 12 weeks (\pm 7 days) thereafter until disease progression. End of Treatment Visit CT/MRI should be performed only for those patients that discontinue treatment for a reason other than disease progression.

An unscheduled scan for suspected disease progression may be performed at any time. However, adherence to the planned imaging schedule is critical regardless of dose delays or unscheduled or missed assessments. Scans will be submitted to an independent central imaging laboratory for assessment by RECIST 1.1 and for determination of measurable disease. Determination of disease progression for clinical management of patients on study will be assessed at the local site. If an initial observation of objective response (CR or PR) is made, a confirmation scan should be done at 6 weeks after initial observation.

At the time of disease progression, if a biopsy is performed, a tumor sample will be collected and sent to the central laboratory, if available. Ensure that the surgical pathology report is submitted with the tumor tissue sample. Refer to the Instruction Sheet for tissue handling instructions for processing and shipping details.

Table 3: Analyte Listing

Chemistry	Hematology	Coagulation	Urinalysis	Other Labs
Sodium	WBC	PT	Specific gravity	Pregnancy test
Potassium	RBC	PTT	pH	ABI-009 PK (central)
Bicarbonate	Hemoglobin	INR	Blood	TSH, T3, T4
Chloride	Hematocrit		Protein	HIV
Total protein	MCV		Glucose	HBV sAg
Albumin	MCH		Ketones	HBV cAb
Calcium	MCHC		Microscopic	HCV Ab
Magnesium	RDW			Total Cholesterol
Phosphorus	Platelets			HDL
Glucose	Differential:			LDL
BUN	-Neutrophils			Triglyceride
Creatinine	-Lymphocytes			Biomarker development (central)
Total bilirubin	-Monocytes			
Alkaline phosphatase	-Eosinophils			
AST (SGOT)	-Basophils			
ALT (SGPT)				
Amylase				
Lipase				

6.3. End of Treatment Visit Assessment

Patient participation is complete after the EOT Visit. The EOT Visit is a safety follow-up visit that is to be performed at least 4 weeks (+ 7 days) after the last dose of ABI-009. All efforts should be made to conduct this visit. If it is not possible to conduct the EOT Visit, documentation of efforts to complete the visit should be provided.

The following procedures will be completed at the EOT Visit as designated in the Schedule of Assessments ([Section 5](#)):

- Physical examination (including physical exam, ECOG Performance Status assessment, weight)
- Vital signs (eg, blood pressure, pulse, respiration rate, temperature)
- Laboratory assessments: chemistry, CBC, differential, platelet count, pregnancy test (women of child-bearing potential, includes tubal ligations)
- Imaging Assessment: CT/MRI is to be performed at the end of study visit only for those patients that discontinue treatment for a reason other than disease progression per RECIST v1.1

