12. Use of strong inhibitors and inducers of CYP3A4 within the 14 days prior to receiving the first dose of ABI-009. Additionally, use of any known CYP3A4 substrates with narrow therapeutic window (such as fentanyl, alfentanil, astemizole, cisapride, dihydroergotamine, pimozide, quinidine, terfanide) within the 14 days prior to receiving the first dose of ABI-009.
13. Known Human Immunodeficiency Virus (HIV).
14. Active Hepatitis B or Hepatitis C.

Length of Study

The study is expected to take approximately 32 months from first patient enrolled to last patient follow-up, including approximately 24 months of enrollment period, an estimated 6 months of treatment (or until treatment is no longer tolerated) and an end of treatment visit at 4 weeks (± 7 days) after last treatment.

The End of Study (EOS) defined as either the date of the last visit of the last patient to complete the study, or the date of receipt of the last data point from the last patient that is required for primary, secondary, and/or exploratory analysis, as pre-specified in the protocol.

End of Treatment (EOT) for a patient is defined as the date of the last dose of ABI-009. End of Treatment Visit for a patient is when safety assessments and procedures are performed after the last treatment, which must occur at least 4 weeks (± 7 days) after the last dose of ABI-009.

Follow-up period is the on-study time period after the EOT Visit. All patients that discontinue study drug and have not withdrawn full consent to participate in the study will continue in the follow-up phase for survival and initiation anticancer therapy. Follow up will continue approximately every 12 weeks (± 3 weeks), until death, withdrawal of consent, or the study closes, whichever is the earliest. This evaluation may be made by record review and/or telephone contact.

Study Treatments

Patients will receive ABI-009 100 mg/m² for 2 of every 3 weeks by IV infusion over 30 minutes. Two dose reduction levels will be allowed: 75 mg/m² and 56 mg/m². Patients will continue to therapy until disease progression, unacceptable toxicity, until in the opinion of the investigator the patient is no longer benefiting from therapy, or at the patients discretion.

Overview of Key Efficacy Assessments

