Due to the extremely rare nature of malignant PEComa, there is very limited information on its incidence. Only one publication has provided an estimate of the incidence of malignant PEComa as 0.012-0.024/100,000 or 0.12-0.24/1,000,000 [10]. Based on this information, it is estimated that there are approximately 42-84 new patients per year in the USA with malignant PEComa. Based on limited information on survival of patients with malignant PEComa [3, 7-9], our estimate for prevalence of malignant PEComa is 0.22-0.48/1,000,000 or approximately 77-168 patients in the USA. A recent report in 2014 [11] reviewed 36 consecutive patients with a diagnosis of malignant PEComa at the Dana Farber Cancer Institute (DFCI) treated in a 5-year period between 2007-2012; the number of cases reported at DFCI is consistent with the estimate above.

Treatment for Malignant PEComa

Currently, no effective medical treatment has been approved for patients with malignant PEComa; therefore it represents a clear unmet medical need and requires the development of effective therapeutic interventions.

The primary treatment option for localized malignant PEComa cases is surgery. However, there is no curative therapeutic option once the disease has spread and it is usually fatal. The majority (~70%) of patients with localized primary malignant PEComas develop metastatic disease over a median follow-up of 1 year [3, 11] and nearly one fifth of the patients have metastatic disease at presentation [11]. Lung, liver, peritoneum, and bones were the most common sites of metastases in an observational study with 36 patients [11]. There is no curative therapy once the disease has spread and it is usually fatal with a median survival of 12-17 months [3, 7-9].

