3.2. Study Duration

The duration of enrollment for this study will last approximately 24 months. A cycle will consist of 3 weeks, with ABI-009 given weekly for 2 weeks followed by a week of rest. Treatment will continue until disease progression or unacceptable toxicity.

It is anticipated that each study patient will be on study for approximately 2 weeks of screening, approximately 6 months of treatment and 4 weeks of safety follow up. The total duration of the study is expected to be approximately 32 months.

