3.3. End of Study, End of Treatment, End of Treatment Visit, Follow-up Period

End of Study (EOS) is defined as either the date of the last visit of the last patient to complete the study, or the date of receipt of the last data point from the last patient that is required for primary, secondary, and/or exploratory analysis, as pre-specified in the protocol.

End of Treatment (EOT) is defined as the date of the last dose of ABI-009 for an individual patient

End of Treatment Visit for a patient is when safety assessments and procedures are performed after the last treatment, which must occur at least 4 weeks (\pm 7 days) after the last dose of ABI-009.

Primary analysis for this study will occur after all patients have either completed the study or completed 6 months of treatment. Patients who are still active at the time of the primary analysis may continue on study until disease progression or medication intolerance is observed.

Primary Completion is the time when the last patient is assessed or receives an intervention for the purposes of final collection of data for the primary analysis.

Follow-up period is the on-study time period after the EOT Visit. All patients that discontinue study drug and have not withdrawn full consent to participate in the study will continue in the follow-up phase for survival and anticancer therapy. Follow-up will continue approximately every 12 weeks (+/- 3 weeks), or more frequently as needed,

until death, withdrawal of consent, or the study closes, whichever is the earliest. This evaluation may be made by record review and/or telephone contact.

The final patient's last visit for the study will be defined as whichever of the following represents the last time point:

- When the last patient on study has completed their Safety follow-up visit, or
- When the last patient on study has documented toxicities to ABI-009 and the toxicity has resolved, returned to baseline or is deemed irreversible after the Safety follow-up visit or
- When the last patient completes or discontinues the follow-up phase

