6.4. Follow-up Period for Survival and Initiation of Anticancer Therapy

Post-treatment survival time and any subsequent anticancer therapy information status will be monitored approximately every 12 weeks (+/-3 weeks) from EOT Visit or more frequently as needed, until death, withdrawal of consent, or the study closes, whichever is earliest. This evaluation may be by record review and/or telephone contact.

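### Section 6.3 ends participation at the End of Treatment Visit, contradicting the survival follow-up required elsewhere; Section 3.2 and the expected 32 months leave that follow-up out of the count

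*Combined protocol and SAP*

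**What the plan says.** Overall survival is a secondary endpoint (Sections 2.2.2 and 10.1.1). It runs from first dose to death from any cause and is censored at last contact (Section 10.5.3).

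**Text that ends participation early or leaves follow-up out**
- Section 6.3: "Patient participation is complete after the EOT Visit". That visit takes place about 4 weeks after the last dose.
- Section 3.2 gives each patient's anticipated time as about 2 weeks of screening, 6 months of treatment and 4 weeks of safety follow-up, then adds: "The total duration of the study is expected to be approximately 32 months".
- The synopsis, in its paragraph on duration, has: "The study is expected to take approximately 32 months from first patient enrolled to last patient follow-up, including approximately 24 months of enrollment period". The other parts named there are an estimated 6 months of treatment and the End of Treatment (EOT) visit at 4 weeks.

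**Text that requires follow-up after the EOT Visit**
- Section 6.4 monitors survival and later anticancer therapy about every 12 weeks (+/- 3 weeks) from the EOT Visit, "until death, withdrawal of consent, or the study closes, whichever is earliest".
- Section 3.3 treats the period after the EOT Visit as on-study time. It lists as one possible last time point for the study: "When the last patient completes or discontinues the follow-up phase".
- The synopsis, the definitions table and Table 2 (survival-status row and footnote e) agree with 6.4.

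**The concern.** Section 6.3 is a procedures section, the part a site works from. Read literally, it tells the site that nothing more is due after the EOT Visit, while the next section says survival contact starts there.

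Disease progression is one of the main reasons for stopping treatment (synopsis, Study Treatments; Section 12.1). A patient dropped about a month after the last dose would often be dropped just after progressing, when the risk of death is rising. Kaplan-Meier estimation assumes that censored patients have the same prognosis as those still followed. That would fail here, and OS would read too high.

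The planned duration shows the same omission. If resources are set from a per-patient time and a study total that leave survival follow-up out, the late enrollees are the ones whose follow-up is at risk. Section 1.1 says of spread disease that "it is usually fatal with a median survival of 12-17 months", so deaths after the EOT Visit carry much of the OS information.

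**Working it through.** **1. Reproduce the 32 months.** Inputs from the synopsis and Section 3.2: enrollment 24 months, treatment 6 months, EOT visit 4 weeks (28/30.44 = 0.92 month), screening 2 weeks (0.46), visit window 7 days (0.23).
- 24 + 6 + 0.92 = 30.9 months
- with screening: 31.4 months
- with the window as well: 31.6 months, or about 32

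The figure is fully used up by enrollment, treatment and the EOT Visit.

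**2. Place the first survival contact of the last patient.** EOT Visit at month 30.9, plus 12 weeks (2.76 months) = month 33.7. With the +/- 3 week window the range is 33.0 to 34.4. All of it lies after month 32.

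**3. What is lost if follow-up really stopped at the EOT Visit.** Assumptions not in the documents: exponential survival; every patient cut off about 7 months after first dose (6 + 0.92); median OS 12 to 17 months; 26 metastatic patients (Section 1.3.1 puts 85-90% of cases as metastatic; of 30 that is 25.5 to 27).
- Proportion dead by 7 months = 1 - 2^(-7/median): 33% at a median of 12, 25% at 17
- Expected deaths in 26: 8.6 and 6.5
- Chance that at least 13 of 26 have died, so that the median is reached: 5.7% and 0.5%

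This measures lost information only, because a fixed cut-off is unrelated to prognosis. The bias from cutting off patients shortly after progression comes on top. Its direction is clear, but its size needs PFS, post-progression survival and the rate of death before progression, none of which the documents give.

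**4. What closure at month 32 would mean with follow-up kept up to that date.** Assumptions: uniform accrual over 24 months, exponential survival, no loss to follow-up, status known at closure. Potential OS time runs from 32 - 24 = 8 months (last patient) to 32 months (first), mean 20. With l = ln 2/median, proportion dead = 1 - [exp(-8l) - exp(-32l)]/(24l). The last two columns come from 4,000 simulated trials of 26 patients, with Brookmeyer-Crowley limits.

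| Median OS (months) | Dead at month 32 | KM median reached | Upper 95% limit estimable |
|---|---|---|---|
| 12 | 66% | 99% | 76% |
| 17 | 54% | 92% | 37% |
| 24 (sensitivity, outside the cited range) | 43% | 68% | 12% |

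Closing at month 32 would usually still give a median, often with an open upper limit. Stopping at the EOT Visit would almost never give one.

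**The case against.** The strongest reply is that no site would act on 6.3. Section 6.4 follows it directly, Table 2 has a survival-status row, and the synopsis, definitions table and Section 3.3 agree. Section 12.2 asks for every effort to collect survival data after a patient leaves treatment, and Section 14.3 allows a search of public records. This makes literal compliance unlikely. It does not remove the contradiction.

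A reader might also infer more than the documents support:
- **That 32 months is a closing date.** Both places call it expected and approximate. Section 3.3 ties End of Study to the last visit or to the last data point required for analyses that include the secondary ones, and Section 10.5.1 provides for an updated report. What stands is that no minimum OS follow-up is stated, so that trigger does not say when OS is complete.
- **That late enrollees add almost no survival time.** OS starts at first dose, so the last patient has about 8 months of potential follow-up at month 32. Contact may also be more frequent than 12-weekly, by telephone or record review, so a check before closure is already permitted.
- **That a median survival of 12-17 months proves 32 months too short.** Section 1.1 counts that figure from diagnosis of advanced disease, not from first dose, and the table above shows that the median would usually be reached.
- **That OS would be overstated by a known amount.** Any such figure would rest on inputs that the documents do not contain.

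Finally, all analyses are descriptive and KM quartiles are promised only where they can be estimated (Section 10.5.1), so an open upper limit is foreseen.

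**Conclusion.** The point holds as a contradiction in current text plus a gap in the planned duration. Section 6.3 cannot stand beside 6.4, 3.3, the synopsis, the definitions table and Table 2. Section 3.2 leaves out time that 3.3 counts as on-study. The 32 months reproduces only without survival follow-up, although the synopsis describes it as running to the last patient's follow-up. That phrase could mean the 4-week safety visit, but the synopsis itself uses the follow-up period for the time after that visit, so the meaning needs stating.

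If 6.3 were followed, OS would be informatively censored and overstated. Under the assumptions in step 3, the metastatic median would be reached in at most about 6% of trials. The size of the bias cannot be derived from the documents. The duration figure is a planning gap and not a strict contradiction. The matter should be corrected, but it does not touch the primary ORR analysis.

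**What to change.** 1. **Section 6.3:** replace the sentence with wording that the treatment period is complete and the patient enters survival follow-up under Section 6.4.
2. **Section 3.2:** add survival follow-up to the per-patient time on study.
3. **Section 3.2 and synopsis:** either restate the total duration to include survival follow-up, or say that 32 months covers only enrollment, treatment and the EOT Visit.
4. **Optional:** state what study closure means for OS, as a cutoff or minimum follow-up of the sponsor's choosing, with a survival check of all living patients at that date. The documents do not require any particular length.

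The cost is wording, and possibly a longer stated duration with further telephone or record-review contacts for about 30 patients. The ORR analysis is not delayed.
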